7.1.1. Packaging and Labeling

All study treatment will be provided by Lilly. Clinical study materials will be labeled according to the country's regulatory requirements.

LY3415244 drug product is a clear to opalescent, colorless to slightly yellow to slightly brown, sterile, preservative-free solution for IV infusion supplied in glass vials.

7.2. Method of Treatment Assignment

Patients who meet all criteria for enrollment will be assigned to receive LY3415244 in this study.

An interactive web-response system (IWRS) will be used to dispense study drugs and to ensure that the correct number of patients is assigned to each cohort.

No dose escalations (that is, to the next cohort) can occur without prior discussion of clinical data and agreement with the responsible Lilly CRP/CRS.

If investigators have eligible patients who have consented concurrently, more than the assigned patients may be entered at a particular dose level provided that accrual has not ceased due to excessive toxicity. This enrollment procedure is allowed because of the advanced disease state of this patient population and the screening involved in defining eligibility. This event should be approved by Lilly following discussions with the investigators.

7.2.1. Selection and Timing of Doses

The doses will be administered at approximately the same times on each day. The actual time of all dose administrations will be recorded in the electronic case report form (eCRF).

A cycle is defined as an interval of 28 days (Q2W regimen) as shown in [Table JZDA.7.1](#). A delay of a cycle due to holiday, weekend, bad weather, or other unforeseen circumstances will be permitted for a maximum of 7 days and not counted as a protocol deviation. The reason for the delay should be documented on the eCRF.

The first study treatment will be administered within 7 days after the patient is assigned to a treatment cohort. There should be a minimum of 14 days between doses of study drug.

A patient may continue to receive LY3415244 until he or she meets one or more of the specified reasons for discontinuation (see [Section 8](#)).

7.2.2. Dose Escalation: Phase 1a

7.2.2.1. Dose Escalation Method

Dose escalation of LY3415244 (at the levels shown in [Figure JZDA.5.1](#)) will be driven by a mTPI-2 method (Guo et al. 2016 [WWW]), taking into consideration available PK and pharmacodynamic data from previous dose levels. Each cohort in this study will contain a minimum of 3 patients.

Like the 3+3 design, the mTPI-2 method incorporates prespecified escalation rules. In contrast, the mTPI-2 method is based on quantitative models that incorporate uncertainty into the decision rules, thereby allowing more precise RP2D selection. If 3 or 6 patients are enrolled in a cohort, the escalation rule parallels a traditional 3+3 design. However, it allows flexible number of patients in a cohort. For example, with 2 DLTs per 6 patients enrolled, the mTPI-2 would recommend staying at the current dose, as analogy to 1 DLT per 3 patients enrolled in 3+3 design; therefore, it allows more patients for a more precise estimate of the DLT rate at this dose level.

[Appendix 7](#) provides the mTPI-2 escalation rules for any cohort size up to 20 patients.

Following a discussion between the Lilly CRP/CRS and the investigators, a more conservative dose selection may be applied to the next cohort (for instance, if PK/pharmacodynamic data suggest that further dose increase would not be expected to yield additional benefit). For example, if the rule indicates “E” to escalate, the dose may stay at the current dose level, be de-escalated to a lower level, or escalation may cease. In the mTPI-2, the cohort size is not fixed. However, each cohort in this study will contain a minimum of 3 patients, unless the escalation rules dictate that the dose should be de-escalated (“D” or “DU”). Doses can be escalated, de-escalated, and re-escalated following the rules in [Appendix 7](#). If the dose decision was “DU,” the dose cannot be re-escalated to that level.

This study is designed to identify a dose level with a dose-limiting target toxicity rate of 30%. The mTPI-2 method considers an equivalence interval (EI) around the target toxicity rate. For this study, the EI is elicited to be (25%, 35%), resulting in the rules in [Appendix 7](#).

Safety data, in particular DLTs, will be the primary criteria for the dose escalation. In addition, if available at the time of dose escalation decision, PK (for example, Cmax, AUC, pharmacodynamics results) will be used as secondary/supporting data for dose escalation.

Intermediate and/or higher dose as well as alternative schedules of administration will be explored if deemed necessary after discussion between Lilly and investigators and taking into account patient safety and PK/PD data. If needed, additional patients may be enrolled to further assess PK/PD or tolerability.

7.2.2.2. Dose-Limiting Toxicity Determination

A DLT is defined as any of the events listed in [Table JZDA](#), if the event occurs during the DLT observation period (Cycle 1) in Phase 1a, and toxicity that is not clearly and directly related to the primary disease or another etiology.

All AEs of Grade 3 or higher that occur during the DLT observation period will be included in the DLT definition except for toxicities with a clear, alternative explanation, including the exceptions listed in Section [7.2.2.2.1](#).

Patients who experience a DLT in Cycle 1 will be discontinued from study treatment.

Table JZDA.7.2. Dose-Limiting Toxicity

Hematologic toxicity

 Grade 3 thrombocytopenia requiring platelet transfusion or Grade 4 thrombocytopenia of any duration Grade ≥ 3 febrile neutropenia Grade ≥ 3 anemia requiring a blood transfusion Other Grade 4 toxicity lasting >7 days, excluding toxicities listed in Section 7.2.2.1
Nonhematologic toxicity – nonlaboratory

 Grade 4 irAE, except as stated otherwise below Grade ≥ 3 colitis or noninfectious pneumonitis Other Grade 3 irAE, excluding colitis or pneumonitis, that: 
 does not downgrade to Grade 2 within 3 days after onset of the event despite optimal medical management including corticosteroid therapy, or does not downgrade to Grade ≤ 1 or the patient's baseline level within 14 days after onset of the event Grade 2 pneumonitis that does not resolve to Grade ≤ 1 within 3 days after initiation of optimal medical management including corticosteroids therapy Grade ≥ 3 toxicity lasting an extended period of time despite optimal supportive care (for example, nausea, vomiting, and diarrhea lasting >3 days) Grade ≥ 3 fatigue lasting >7 days Grade ≥ 3 hypertension despite of maximal medical therapy
Nonhematologic toxicity – laboratory/investigations

 Grade 3 or 4 amylase or lipase elevation that leads to discontinuation of study drug Other Grade 3 or 4 laboratory value lasting >14 days or requiring medical intervention ALT or AST: 
 $>8 \times$ ULN, if the patient does not have HCC or liver metastasis ≥ 2-fold above the patient's baseline value that lasts >7 days, if the patient has HCC or liver metastasis and had ALT or AST $>3.0 \times$ ULN at baseline $>3 \times$ ULN with concomitant bilirubin $>2 \times$ ULN, in the absence of cholestasis Total bilirubin $>3 \times$ ULN
Other hematologic or nonhematologic toxicity

 Grade 5 toxicity (that is, death) Toxicity deemed by the investigator and Lilly CRP/CRS to be dose limiting, such as: 
 toxicity that is possibly related to study treatment and requires discontinuation of the patient from the study at any time during Cycle 1, or persistent Grade >2 toxicities causing a delay of >14 days in initiating Cycle 2

Abbreviations: AE = adverse event; ALT = alanine transaminase; AST = aspartate transaminase; CRP = clinical research physician; CRS = clinical research scientist; HCC = hepatocellular carcinoma; irAE = immune-related adverse event; IV = intravenous; ULN = upper limit of normal.

7.2.2.2.1. Events That Are Not Considered to Be DLTs

The following events listed in this section will not be considered to be DLTs:

- Adverse event that is clearly and directly related to the primary disease or to another etiology
- Known class effects that have been observed with immunotherapy:
 - Grade 3 endocrine disorder (thyroid, pituitary, and/or adrenal insufficiency), if both the following criteria are met:

- the disorder is manageable with or without systemic corticosteroid therapy and/or hormone replacement therapy, and
- the patient is asymptomatic
- Grade 3 inflammatory reaction attributed to a local antitumor response (such as, inflammatory reaction in the lymph nodes or at sites of metastatic disease)
- Any grade vitiligo or alopecia
- Grade 3 or 4 lymphopenia
- First occurrence of Grade 3 infusion-related reaction (IRR) during infusion of LY3415244, if both of the following criteria are met:
 - the patient did not receive corticosteroid prophylaxis, and
 - the Grade 3 IRR resolves within 6 hours with appropriate clinical management

If symptoms reappear, the event would be considered a DLT.

- Grade 3 or 4 neutropenia meeting both of the following criteria:
 - not associated with fever or systemic infection, and
 - improves by at least 1 grade within 7 days with treatment
- In order to exclude potential detection of electrolyte abnormalities that cannot be associated with clinical signs of symptoms, or laboratory test error. Isolated Grade 3 electrolyte abnormalities meeting both of the following criteria:
 - not associated with clinical signs or symptoms, and
 - reversed with appropriate maximal medical intervention within 2 days

It should be recognized that for patients who have received prior immune therapy, including check point inhibitor therapy, there is the potential for delayed manifestation of serious irAEs such as colitis, hepatitis, pneumonitis, and endocrinopathies. Patients manifesting potential delayed irAEs should receive prompt evaluation and treatment. .

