7.4. Dose Modification

No dose modification is allowed during Phase 1a DLT observation period (Cycle 1).

After the Phase 1a DLT observation period (Cycle 1), doses of the study drug may be delayed or discontinued to manage specific AEs or other toxicities. Dose reductions are not permitted. All dose modifications should be documented, including the approach taken and a clear rationale for the need for modification.

The investigator must assess whether the toxicity is at least possibly due to study treatment and apply the dose-modification guidelines. Investigators are encouraged to consult Lilly for additional guidance.

If a patient requires a dose delay, study treatment should be resumed within 1 cycle, if possible and appropriate. If study treatment cannot be resumed within 1 cycle, every effort should be made to restart on the first day of the next cycle. In rare circumstances, a delay of >28 days may be permitted before permanent treatment discontinuation, as long as the patient demonstrates clinical benefit, does not have objective progression, and is recovering from the toxicity. Such circumstances must be discussed with the Lilly CRP/CRS.

Adverse events of immune-related etiology are expected because of the study drug's mechanism of action and may occur shortly after the first dose or several months after the last dose. Study treatment must be withheld if the patient experiences a drug-related toxicity or a severe or life-threatening AE. Dose reductions are not permitted.

A 4-hour observation period is required after the administration of LY3415244 in Cycles 1 to 3. During observation period, patients treated with LY3415244 should be closely monitored for signs and symptoms indicative of an infusion-related reaction by medical staff from the start of the infusion until 4 hours after the end of the infusion, in an area where emergency medical resuscitation equipment and other agents (epinephrine prednisolone equivalents, etc.) are available. LY3415244 infusion-related reactions will be defined according to the Common Terminology Criteria for Adverse Events (CTCAE), Version 4.0 definition of IRRs.

Table JZDA.7.3 presents instructions for management of infusion-related reactions associated with LY3415244.

Table JZDA.7.3. Management of Infusion-Related Reactions

Grade	Management
2	First occurrence

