	
Stop the infusion and proceed with following:
 
 1. If resolved to Grade 0 or 1 within 1 hour after stopping the infusion 
 a. restart the infusion at 50% of the original rate (for example, reduce from 100 to 50 mL/hr) 2. If NOT resolved to Grade 0 or 1 within 1 hour after stopping the infusion: 
 a. delay study treatment until the symptoms resolve in \leq48 hours, and b. premedicate prior to the next scheduled dose. Premedication should be administered 1.5 hours (\pm30 minutes) prior to the LY3415244 infusion with diphenhydramine (or other antihistamine), acetaminophen (or other antipyretic), steroids etc., at the discretion of treating physician.
3 or 4	
Second occurrence
 
Immediately and permanently discontinue study treatment
 
Immediately and permanently discontinue study treatment.
 
Patients who experience a Grade 3 IRR that resolves within 6 hours may continue on study treatment. For subsequent infusions, the patient should be premedicated 1.5 hours (\pm30 minutes) prior to the LY3415244 infusion with diphenhydramine (or other antihistamine), acetaminophen (or other antipyretic), steroids etc., at the discretion of treating physician.
 
If symptoms reappear, immediately and permanently discontinue study treatment.

Table JZDA.7.4 presents guidance for irAE management (including use of corticosteroids) and criteria for dose delays and discontinuations if the patient experiences a potential irAE considered at least possibly related to LY3415244.

Because of the potential for rapid and serious sequelae associated with irAEs, early intervention with corticosteroids is encouraged, concurrent with further diagnostic medical evaluations for possible nonimmune-related causes of AEs. The treatment plan should always include a thorough workup of the issue to rule out other potential etiologies such as infection. Guidelines used by local standards such as, but not limited to Haanen and colleagues (2017), Puzanov and colleagues (2017), or Brahmer and colleagues (2018), supersede the guidelines provided in Table JZDA.7.4 if deemed appropriate by the investigator. If a patient experiences an irAE that is not listed in this table, consult the Lilly CRP/CRS to discuss appropriate management.

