8.1. Discontinuation from Study Treatment

Patients will be discontinued from study treatment in the following circumstances:

- the patient is enrolled in any other clinical study involving an investigational product or any other type of medical research judged not to be scientifically or medically compatible with this study.
- the patient becomes pregnant during the study
- the patient is significantly noncompliant with study procedures and/or treatment as described in Section 7.6
- The patient experiences a DLT (see Section 7.2.2.2) during Cycle 1, a DLT-equivalent toxicity (see Section 7.2.2.2.2), or other unacceptable toxicity
- the patient requires a dose delay of >28 days, except as described in Section 7.4
- the patient, for any reason, requires treatment with another therapeutic agent that has been demonstrated to be effective for treatment of the study indication.
Discontinuation from study treatment will occur prior to introduction of the new agent
- the investigator decides that the patient should be discontinued from study treatment
- the patient requests to be discontinued from study treatment
- the patient has received the maximum duration of 12 months of study treatment (longer duration may be considered for a patient receiving clinical benefit, in consultation with the Lilly CRP/CRS). If tumor imaging shows initial disease progression, at the discretion of treating physician, patients may remain on study treatment with repeat imaging 4 to 6 weeks later to assess tumor response or confirm progression per RECIST 1.1 with confirmatory scan on disease progression

Patients who are discontinued from study treatment will have follow-up procedures performed as shown in the Schedule of Activities (Section 2).

Discontinuation of study treatment may be considered for patients who meet all of the following criteria:

- have a confirmed CR, **and**
- have received study treatment for at least 24 weeks, **and**
- have received at least 2 cycles of study treatment beyond the date when the initial CR was declared.

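### Table JZDA.7.3 lets a patient continue after a brief Grade 3 infusion reaction that, in Cycle 1 of Phase 1a, can be a DLT requiring discontinuation

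*Protocol*

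**What the plan says.** Four parts of the protocol bear on this.

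- **DLT definition (7.2.2.2).** "All AEs of Grade 3 or higher that occur during the DLT observation period will be included in the DLT definition", apart from events with a clear alternative explanation and those listed in 7.2.2.2.1.
- **IRR exemption (7.2.2.2.1).** The exempt event is "First occurrence of Grade 3 infusion-related reaction (IRR) during infusion of LY3415244, if both of the following criteria are met". The two criteria are no corticosteroid prophylaxis and resolution within 6 hours. If symptoms return, the event becomes a DLT.
- **Consequence (7.2.2.2 and 8.1).** "Patients who experience a DLT in Cycle 1 will be discontinued from study treatment". Section 8.1 lists the same ground for stopping: "The patient experiences a DLT (see Section 7.2.2.2) during Cycle 1, a DLT-equivalent toxicity (see Section 7.2.2.2.2), or other unacceptable toxicity".
- **IRR management (7.4, Table JZDA.7.3).** The Grade 3 or 4 row first orders permanent discontinuation, then adds: "Patients who experience a Grade 3 IRR that resolves within 6 hours may continue on study treatment". It goes on to describe premedication for later infusions.

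Section 7.4 also requires monitoring for IRRs in Cycles 1 to 3 "from the start of the infusion until 4 hours after the end of the infusion", so it anticipates reactions that begin after dosing has finished. The SAP (5.12.2) refers back to the protocol for the DLT definition and adds nothing on this point.

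**The concern.** The exemption and the table share the 6-hour resolution condition but not the others. The exemption also requires onset during the infusion and no steroid prophylaxis. The table requires neither, is not limited by cycle, and does not refer to DLT status. For events between the two, the general rules say stop and the IRR-specific instruction says the patient may go on.

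Two things are at stake. The first is direct: Day 15 lies inside Cycle 1, so a patient with such a reaction on Day 1 could be dosed again after a protocol-defined DLT. The second is indirect: staff who treat the event as one that allows continuation may also not record it as a DLT, and the DLT count drives the mTPI-2 decision for that dose level.

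**Working it through.** **1. Classifying a Grade 3 IRR in Cycle 1 of Phase 1a that resolves within 6 hours**

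| First Grade 3 IRR | Exempt under 7.2.2.2.1? | 7.2.2.2 and 8.1 | Table JZDA.7.3 |
|---|---|---|---|
| During infusion, no steroid prophylaxis | Yes | Not a DLT | May continue |
| During infusion, after steroid prophylaxis | No | DLT, discontinue | May continue |
| Starts after dosing ends | No | DLT, discontinue | May continue |

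The first row is consistent; the other two are not.

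**2. Where the conflict stops.** After Cycle 1 and in Phase 1b, the relevant term is DLT-equivalent toxicity, which must be an event listed in Table JZDA.7.2. A brief Grade 3 IRR is not listed there, so the table's permission stands.

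**3. Exposure to the gap.** Table JZDA.7.1 gives 2 administrations in Cycle 1, Day 1 and Day 15, each followed by 4 hours of observation.

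- Observed time after dosing: 2 × 4 h = 8 h per patient.
- With a 60-minute infusion: 4 h of 1 + 4 = 5 monitored hours per dose.

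These are shares of monitoring time, not of reactions. The Synopsis plans about 27 to 30 Phase 1a patients.

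**4. Direct effect.** Further Cycle 1 doses after a Day 1 event: 0 under 7.2.2.2 and 8.1, and 1 under the table.

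**5. Indirect effect, if the event is also not counted.** Under 7.6.1.1 a patient is DLT-evaluable either with a DLT after at least one dose or without one after all assigned doses. The number of evaluable patients therefore stays the same and only the DLT count falls by one. Appendix 7, up to the maximum of 10 patients per level (5.2), reads:

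| Patients | 0 DLTs | 1 DLT | 2 DLTs |
|---|---|---|---|
| 3 | E | S | D |
| 4 | E | S | D |
| 5 | E | E | D |
| 6 | E | E | S |
| 7 | E | E | S |
| 8 | E | E | S |
| 9 | E | E | E |
| 10 | E | E | E |

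These cells were re-derived from the mTPI-2 rule with target 0.30 and equivalence interval 0.25 to 0.35 (7.2.2.1). A Beta(1,1) prior and a 0.95 cutoff for DU were assumed. With x DLTs in n patients the posterior is Beta(1 + x, 1 + n − x). The decision follows the interval, in steps of 0.10, with the largest posterior probability divided by width. For 1 DLT in 3 patients the posterior is Beta(2,3), with F(p) = 6p² − 8p³ + 3p⁴:

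- 0.15 to 0.25: (0.2617 − 0.1095)/0.10 = 1.52
- 0.25 to 0.35: (0.4370 − 0.2617)/0.10 = 1.75
- 0.35 to 0.45: (0.6090 − 0.4370)/0.10 = 1.72

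The equivalence interval is highest, so the decision is Stay, as Appendix 7 states. All 24 cells agree.

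Reading one column to the left gives the effect of an uncounted event:

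- **It is the only DLT:** Escalate instead of Stay at 3 or 4 patients; no change at 5 to 10.
- **There is one other DLT:** Stay instead of De-escalate at 3 or 4; Escalate instead of De-escalate at 5; Escalate instead of Stay at 6 to 8; no change at 9 or 10.

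**The case against.** The strongest argument is that the event may not be a DLT at all. The opening sentence of 7.2.2.2 ties DLTs to Table JZDA.7.2, which lists no IRR, and that table's general Grade 3 item requires a prolonged toxicity. It is true that DLT status rests on the catch-all sentence and that 7.2.2.2 is not perfectly consistent. But the catch-all is explicit. The exemption, and its line turning a recurrence into a DLT, would also serve no purpose if Grade 3 IRRs did not otherwise count.

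Second, the protocol arguably settles the matter already. Section 8.1 is mandatory, the table only permits, and 7.2.1 says "A patient may continue to receive LY3415244 until he or she meets one or more of the specified reasons for discontinuation". A site that discontinues satisfies every section. This stands: discontinuation is the better reading. Section 7.4 also bars dose modification in Cycle 1, although continuing at the same dose is not clearly a modification. What remains is that the instruction a site would consult for an IRR grants a permission that the general rule withdraws, without saying so.

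Third, the Appendix 7 effect needs a separate classification error that survives review. This also stands. Escalation requires discussion with the sponsor's physician (7.2), data are reviewed cohort by cohort (9.4.2, 10.3.4), and any IRR triggers extra blood samples (Appendix 4). Those checks may correct the count, but none is required before an individual patient's Day 15 dose.

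**Conclusion.** The concern holds and is minor. In Cycle 1 of Phase 1a, at any dose, Table JZDA.7.3 permits continuation after some Grade 3 IRRs for which 7.2.2.2 and 8.1 require discontinuation. The supported effect is one Day 15 dose, in a patient who should receive none, after a Day 1 event. The shift in the escalation decision is conditional on the event also being missed as a DLT at cohort review.

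The conclusion rests on taking the catch-all sentence in 7.2.2.2 at its word and on reading the exemption's timing condition literally; nothing in the protocol widens it to the observation period. The documents give no IRR rate and none is assumed, so the number of patients affected cannot be estimated.

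**What to change.** Add one sentence to the Grade 3 row of Table JZDA.7.3:

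> In Cycle 1 of Phase 1a this applies only to a Grade 3 IRR that meets the exemption in Section 7.2.2.2.1; any other Grade 3 IRR in that period is a DLT and Section 8.1 applies.

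Leave the rule for later cycles and Phase 1b as it is. The change needs no new procedures. It makes the catch-all reading of 7.2.2.2 explicit for IRRs, and the only permission it removes is one that 7.2.2.2 and 8.1 already override.

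If the sponsor instead intends brief post-infusion Grade 3 IRRs to be exempt, the timing condition in 7.2.2.2.1 is the text to change. That is a clinical choice.
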